#### Projected number of subjects who will be enrolled to obtain required number of completers

75

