This procedure is based on our previous experience acquired during protocol NYSPI IRB 6013 (mifepristone study for cocaine dependence) with patients who cannot participate in the inpatient procedure. Over a period of 7 days, not counting Saturdays and Sundays, a participant will have to produce at least three consecutive cocaine negative urine toxicologies at daily visits. Once abstinence is established the phase 1 procedures begin (Table 1), with verification of negative toxicology before each testing day. Randomized medication will begin after completion of all the physiological tests.

---

If a urine toxicology test emerges positive for cocaine once Phase-1 procedures have begun, the testing will stop. The patient can then attempt another period of seven days to reach abstinence, complete the baseline testing, and begin randomized medication. If abstinence cannot be reached during this two-week window, the patient will be offered to carry out phase 1 as an inpatient. If the patient cannot participate as an inpatient, referrals to other treatment options will be offered.

Phase 2, outpatient phase, week 2 to 7, cocaine-dependent patients only

During this phase in which only cocaine-dependent patients participate, they will continue randomized medication while participating in a structured program to support and promote continuing abstinence and completion of the study.

For patients continuing at the STARS clinic and DOSA at Waters Place ([name]), the structure of the program during this phase will be as follows:

- 1: Patients continue to receive intranasal Oxytocin (24IU/day) vs. intranasal placebo. During their visits to either clinic, they will administer the randomized medication under supervision from a bottle kept at the clinic. Each witnessed administration will be recorded. Since they "self-administer" the medication, it can be witnessed by any member of the research team.

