3.4.3. Intent to Treat/ Dropouts and missing data: All primary analysis will be on Intent-to-Treat (ITT) sample, i.e. all subjects from COC and CON groups in Phase 1 (50 per arm) and all subjects randomized to OT and PBO groups in Phase 2 (25 per arm). [In Phase 1, we expect little attrition. Measures as described (3.4.1) will provide usable data after 2 days of measurements. For phase 2, we anticipate an attrition rate of 30%, leaving approximately 18 completers per arm.] If a patient drops out during Phase 2, the maximum number of consecutive abstinent days achieved in the trial will be considered as primary outcome. The inferences from analyses with missing data are considered valid provided that they are "missing at random" (Little and Rubin 1987). One can assume either parametric or semi-parametric models for missingness (Diggle and Kenward 1994; Kenward 1998; Liu et al 1999; Rotnitzky et al 1998). Inferences from various models of missingness provides a measure of the efficacy estimate from each models.

3.4.4. Significance testing and preliminary analyses: All tests for main effects will be performed at two-tailed significance $\alpha=5\%$. Before performing specific analyses (described below), we will examine all variables for outliers and normality. Demographic variables (ethnicity, gender, age) and baseline measures in the groups will be described in terms of means, standard deviations, proportions and 95% confidence intervals. The covariates (Section 3.4.1) will be included if they are found to affect outcome measures.

Hypotheses:

Primary Aim 1 [Phase 1]: The goal of primary aim 1 is to investigate the effect that both IN DDAVP and OT have on stress sensitivity. **Primary Aim 1a, hypothesis 1:** IN DDAVP will be associated with greater secretion of ACTH and subjective ratings in cocaine dependent patients compared to control patients. **Primary Aim 1b, hypothesis 2:** IN OT treatment will significantly reduce the secretion of ACTH and subjective ratings associated with IN DDAVP in cocaine dependent patients compared to control patients. The differences based on the outcomes specified in hypotheses 1 and 2 between the subjects in COC and CON groups will be examined using parametric or non-parametric matched sample test.

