Primary Aim 2 [Phase 2]: The goal of primary aim 2 is to investigate the effect of OT on cocaine use after abstinence induction. **Primary Aim 2, hypothesis 1:** Cocaine-dependent patients receiving IN OT will display significantly more days of consecutive abstinence after abstinence induction compared with IN placebo at the end of the study. The effect of IN OT treatment (based on groups) on the primary outcome (maximum number of consecutive abstinence days for each patient) will be analyzed using generalized linear models (PROC GLIMMIX in SAS®) with main effect of randomization assignment (OT vs. PBO).

Secondary Hypotheses: We will examine the feasibility, safety, tolerability, and potential efficacy of IN OT for relapse prevention in cocaine dependence. 2.1): Cocaine-dependent patients receiving IN OT who complete all 6 weeks of phase 2 will tally fewer cocaine using days than placebo patients who complete all 6 weeks. 2.2): Cocaine-dependent patients receiving OT who relapse will tally fewer cocaine using days than patients receiving placebo who relapse. Regression analysis will be implemented using those who complete (2.1) and those who relapse (2.2) to test the effect of OT on the secondary outcome (cocaine using days).

Exploratory Aims: We will investigate a) if the acute reduction in stress sensitivity with IN OT in Phase 1 or at the end of Phase 2 (repeat IN DDAVP challenge) is associated with a greater number of days of continued abstinence from cocaine in Phase 2; b) if there are gender effects on the primary outcomes.

Power Analysis: **Primary aim 1:** With 50 cocaine dependent subjects and 50 matched controls, we have 50 matched pairs which give us at least 80% power to detect a significant difference between groups using 2-sided hypothesis test at a 5% level of significance for an effect size $\geq .41$. This is considered a small/medium effect size (Araya et al., 2006; Simeon et al., 2011), which are reasonable to expect based on the existing literature. **Primary aim 2:** In Phase 2, we randomize 50 participants into 2 groups (25 in PBO and 25 in OT). The comparison will achieve at least 80% power (testing 2-sided hypothesis of difference at 5% significance) when detecting an effect size ≥ 0.8 . This is a medium effect size that we based on existing relapse studies in cocaine dependence (Back et al., 2010).

Primary outcome:

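### Phase 1 is declared intent-to-treat on all subjects, but the only named test uses complete matched pairs and no covariates; a mixed model on all participants would fit the plan better

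*SAP*

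**What the plan says.** SAP 3.4.3 sets the population: "All primary analysis will be on Intent-to-Treat (ITT) sample, i.e. all subjects from COC and CON groups in Phase 1 (50 per arm"). It expects little attrition in Phase 1, gives no rate, and adds a general missing-at-random statement without naming a model for Phase 1.

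SAP 3.4.4 (Primary Aim 1), repeated in the protocol's Specific Aims, gives the method: group differences for both hypotheses "will be examined using parametric or non-parametric matched sample test". The SAP Power Analysis rests on intact pairs: "we have 50 matched pairs which give us at least 80% power to detect a significant difference between groups", two-sided at 5%, for an effect size of at least 0.41.

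SAP 3.4.1 defines the Aim 1b outcomes as differences between the desmopressin-alone day and the oxytocin-pretreated day, and says the subjective-rating difference is controlled for last day of use. SAP 3.4.4 adds that covariates enter if they are found to affect the outcome.

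On missing sessions, the protocol's outpatient version of Phase 1 says: "If a urine toxicology test emerges positive for cocaine once Phase-1 procedures have begun, the testing will stop". A further seven-day attempt follows, then an inpatient offer, then referral elsewhere.

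On numbers, SAP 3.4.2 enrols 100 in total (50 + 50). The protocol's Description of Subject Population lists 75 under "Projected number of subjects who will be enrolled to obtain required number of completers" for each sample, with 50 completers required.

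**The concern.** The declared population and the named test do not match. A paired t or signed-rank test works on within-pair differences. A participant whose partner lacks the value has no difference to contribute, so the analysis carried out would be a complete-pair analysis rather than one on all subjects. No rule says what happens to a broken pair or when pairs are fixed.

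The requirement differs by aim. Aim 1a needs the desmopressin-alone session from both members. Aim 1b needs both sessions from both members and is the more exposed. Among patients in the outpatient version, a missing session can be tied to cocaine use during testing, so complete pairs may be a selected set.

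The second mismatch is covariates. Neither paired test accepts them, so the plan already needs a model that it does not name.

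At stake are the population behind a primary aim and some power.

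**Working it through.** **Inputs.** 50 pairs, two-sided 5% and effect 0.41 (SAP Power Analysis); all subjects, 50 per arm (SAP 3.4.3). The documents give neither a Phase 1 loss rate nor a within-pair correlation, so both are assumed over ranges.

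**1. Reproduce the stated power.** Paired t test, noncentral t with n − 1 degrees of freedom and noncentrality 0.41·√n. For n = 50 this is 0.41 × 7.071 = 2.899, and power is 81.1%. The plan's figure of at least 80% reproduces with 0.41 read as the mean pair difference divided by the SD of pair differences. Two independent groups of 50 with a difference of 0.41 SD would give 52.8%, so the stated power depends on the paired reading.

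**2. Slack, and assumed loss of pairs (same exact t calculation).**

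| Complete pairs | Pairs lost | Power |
|---|---|---|
| 50 | 0 | 81.1% |
| 49 | 1 | 80.3% |
| 48 | 2 | 79.4% |
| 45 | 5 (10%) | 76.7% |
| 40 | 10 (20%) | 71.5% |
| 35 | 15 (30%) | 65.4% |

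**3. What keeping unpaired participants recovers.** Suppose a fraction q of each group lacks the needed value, independently, among 50 fixed pairs. Complete pairs are m = 50(1 − q)², and unpaired participants on each side are u = 50q(1 − q). With within-pair correlation ρ, generalised least squares on everyone carries the information of m + u(1 − ρ) complete pairs. Both analyses are put on the same normal approximation, power = Φ(0.41·√n − 1.96), because the exact t and the normal approximation differ by about 2 points here and must not be mixed.

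- q = 10%: m = 40.5, u = 4.5. Complete pairs only: Φ(2.609 − 1.96) = 74%. All participants: 40.5 + 4.5 = 45 effective pairs at ρ = 0 (79%), and 40.5 + 2.25 = 42.75 at ρ = 0.5 (76%).
- q = 20%: m = 32, u = 8. Complete pairs only: Φ(2.319 − 1.96) = 64%. All participants: 32 + 8 = 40 effective pairs at ρ = 0 (74%), and 32 + 4 = 36 at ρ = 0.5 (Φ(2.460 − 1.96) = 69%).

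The gain is therefore about 2 to 4 points at 10% and 5 to 10 points at 20%. It is only part of what was lost, because the missing values themselves are not recovered.

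**4. Enrolment figures.** The SAP total is 50 + 50 = 100; the protocol total is 75 + 75 = 150 for 50 + 50 completers. If 75 per sample are enrolled, all subjects is no longer 50 per arm. If 100 are enrolled, there is no allowance for loss.

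**The case against.** The strongest reply is that the loss may be small and is partly provided for. The protocol enrols 75 per sample so that 50 complete; if 50 complete pairs result, power is 81.1% and nothing is lost. A positive urine is not by itself an exit, since a second attempt and an inpatient stay follow, and the stopping rule sits in the outpatient option. The missing-at-random text in SAP 3.4.3 leaves room for a model. The named test also keeps a non-parametric option, which a normal-theory model gives up. All of this stands, and it makes the power loss conditional. It does not supply a broken-pair rule or a place for covariates, and 50 completers per group are 50 complete pairs only if completers are matched with completers.

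A reader might infer more than the documents support:

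- *That one third of Phase 1 sessions will be lost, because 75 are enrolled for 50.* The allowance is meant to leave 50, so it cannot be taken off the 50 again. Participants at the second site sign the study consent at screening, so the 75 may include screen failures who never had a session.
- *That every lost person also discards a partner's data.* This is certain only if pairs are fixed before testing ends. The protocol (Gender and Ethnic Breakdown) describes choosing controls against a table of the patients' demographics, so re-matching may be possible; no passage says.
- *That a pair missing any session is lost to both aims.* A pair with both desmopressin-alone sessions still counts for Aim 1a.
- *That the 26 randomised patients reported at the end of the SAP show pair loss.* That is a Phase 2 number and gives no count of Phase 1 pairs.

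**Conclusion.** The point holds in a limited form. The Phase 1 population (everyone) and the Phase 1 test (complete pairs, no covariates) do not fit together, and nothing in the SAP resolves this. The stated power is correct for 50 complete pairs but tolerates the loss of only one. Under assumed pair losses of 10% to 30% it would be 76.7% to 65.4%. These are scenarios, not forecasts, and the documents do not show that power will in fact fall below 80%. A model on all available participants would recover roughly 2 to 10 points over the ranges examined, assuming independent loss at equal rates in both groups, pairs fixed in advance, and within-pair correlation between 0 and 0.5. Its main merit is agreement with the population, covariates and missing-at-random assumption the SAP already declares. This is a worthwhile correction to a primary aim, not a flaw that invalidates it.

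**What to change.** Make the Phase 1 primary analysis one linear mixed model per outcome on all participants with any session: fixed effects for group, session and group-by-session; random effects for participant and matched pair; age, gender and the stated covariates. Aim 1a is the group contrast on the desmopressin-alone session, and Aim 1b is the interaction. Last day of use and the other cocaine variables exist only for patients, so the SAP should say how they are coded for controls (for example, centred among patients and set to zero in controls). Transform the ACTH area under the curve if it is skewed.

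Keep the paired t or signed-rank test on complete pairs as a sensitivity analysis, and report the number of complete pairs for each aim. State when pairs are fixed and how a broken pair is handled. Restate the Aim 1 power as conditional on 50 complete pairs, and reconcile the SAP's 100 enrolled with the protocol's 75 per sample for 50 completers.

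The cost is SAP wording and modest programming, with no new data. With 50 complete pairs and no covariates the answer should be close to that of the paired test. The downside is reliance on a normal-theory model and on missing-at-random; SAP 3.4.3 already makes the second assumption, and the signed-rank sensitivity analysis guards against the first.

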**Create or insert table to describe the inclusion criteria and methods to ascertain them**

INCLUSION CRITERION	METHOD OF ASCERTAINMENT
1.Age 18 to 60.	MINI interview, self-report, ID confirmation
2. Meets DSM IV criteria for current cocaine	MINI Interview, self

dependence and is seeking treatment.	report
3. Displays at least one cocaine-positive urine toxicology during screening.	Urine Toxicology
4. Use of cocaine at least 4 days in the past month, with at least weekly use, or reports episodic binges of large amounts of cocaine (at least \$200) at least 2x/month.	Self report
5. Able to give informed consent and comply with study procedures.	MINI, Self-report, MSE
6. Can pass the blindfolded scent test recognizing the scent of cinnamon or coffee.	Scent test

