4. Oxytocin: Oxytocin is used during labor and delivery to promote uterine contraction. In this instance, doses vary, but far exceed the daily dose of 24 IU/day used in this study. Administered intravenously as Pitocin, it can also lead to hyponatremia, arrhythmia, convulsions, chest pain, shortness of breath, confusion, swelling, headache, nausea/vomiting, cardiac arrhythmia. During their participation, control participants will receive 2 consecutive doses of IN oxytocin (40 IU in total) during phase 1. Cocaine-dependent patients receive 47 doses of IN oxytocin (940 IU) over a period of 7 weeks. No serious adverse events arose in a study during which 40 IU were administered daily for one week, then 80IU/day for another 7 weeks (Modabbernia et al., 2013). Feeling too relaxed, light-headedness, anxiety, clouded thinking, and nasal cavity irritation are the most common side effects reported in protocols approximating the one presented here (Rodrigues et al., 2009; Ditzen et al., 2009).
  
5. Another potential risk, especially for intranasal cocaine users, is whether the use of the intranasal approach would serve as a trigger for cocaine use. As this pharmacological approach has not been investigated before, this will be specifically queried for during clinic-based administration.
  
6. No data exists examining the risk of cocaine use is enhanced by concomitant intake of oxytocin. We

---

do not anticipate that it would increase the risk of cocaine use. As change in cocaine use is a main outcome of the study, evidence of increased cocaine use will be monitored closely.

7. The stress challenge may cause patients to experience cravings for cocaine. After each procedure, a gradual muscle relaxation procedure will be used to reduce these.
  
8. Vouchers could be exchanged for drugs, or their monetary value could serve as a trigger to procure cocaine. Expending vouchers is a major topic of the counseling during the study to promote a drug-free lifestyle.
  
9. The structured interviews, self-reports, and questionnaires should not pose a physical risk. Their disadvantage is the time to complete them. Our past experience using these measures indicates that patients find them acceptable.
  
10. The risk of the blood tests is the discomfort associated with venipuncture, and a possibility of slight bruising. For the stress challenge, a saline lock will be placed to avoid repeated venipuncture.
  

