Study Assessments: (Table 1). **Physiological tests:** 1) *urine toxicology:* this will be estimated qualitatively at every visit by dipstick (Iscreen™, 9 drugs) which indicates the presence of cocaine, amphetamine, metamphetamine, cannabis, methadone, morphine, oxycodone, barbiturate, benzodiazepine. 2) *stress sensitivity testing:* as outlined in table 2, it is performed on two separate days, [in counterbalanced order.] Day 1: an endocrine challenge with IN DDAVP 80IU (de Goeij et al., 1991). After establishing baseline ACTH secretion, serum samples are taken at time points extending to 90 minutes. The DDAVP challenge is also repeated at the end of phase 2, to see if ACTH secretion is affected by 6 weeks of IN OT administration. Day 2 tests if pretreatment with IN OT treatment can acutely dampen the effect of DDAVP on ACTH secretion. After baseline is measured before and after IN OT, serum samples for ACTH are taken at time points extending to 90 minutes. Serum samples are spun, frozen at -20 Celsius, packed in dry ice, and shipped to the Nathan Kline Laboratory in Orangeburg, NY. 3) Medical monitoring: week 2,4,6: Na, K, Cl, CO3, spot cortisol, β-HCG for women. **Clinician Interviews:** 1) TLFB (Litten and Allan, 1992; baseline, each visit in phase 2). This is an adaptation of the alcohol TLFB, which estimates cocaine use in the past 30 days at baseline, and is then repeated at every visit with the aid of a calendar to obtain a day-by-day registry of cocaine use during phase 2. 2) CGI-O, (Guy, 1976; baseline, weekly during phase 2) the severity and improvement scales measure the overall clinical status of the subject and change from baseline. 3) BAS (Chaplin et al., 2010). This scale is used during stress sensitivity testing. Research staff rate participants on 13 items of behavior relating to arousal during the stress challenge. 4) Adverse event form is a check-list of side effects experienced by participants; 5) HamD, (Williams, 1988; baseline, each wk in phase 2). Estimates 25 depression symptoms. **Self reports:** 1) PSS (Cohen et al., 1983; baseline, weekly during phase 2) measures monthly situations in a subject's lives deemed stressful. Ten questions are scored between 0 (never) to 4 (very often). Modified, it will be administered weekly during phase 2, [and will include a open-ended question inquiring about any adverse life event in the past week.] 2) *Subjective ratings of cocaine craving, depression, anxiety, stress during stress testing (Likert scale 0 to 10, 10 = worse), performed during stress sensitivity testing.* 3) CCS (Weiss et al., 1997) 3-item questionnaire rating cravings for cocaine on a scale of 0 (none) to 9 (Strong).

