
3.3 Compensation and data management.

For phase 1, control participants will receive \$150 for their participation; cocaine-dependent patients will receive \$20/day, or will receive \$150 if they complete the whole week. [During phase 2, cocaine-dependent patients accumulate vouchers for completing all study procedures (Bringing home bottle, assessments, study visits).] Each visit with all study procedures completed will earn them \$5. They can also earn \$20 for each week of consecutive and complete participation. Transportation costs are covered (\$5/visit). Total earnings can reach \$450. StudyTrack, a software system for clinical trials will be used for data management.

3.4 Statistical Analysis:

3.4.1. Outcome measures: PHASE 1: **Primary outcomes:** 1) secretion of ACTH (continuous measure of area from the concentration-time curve (AUC) using trapezoid method, pg/mL/min). 2) subjective rating of cocaine craving, stress, depression, anxiety (continuous) 3) difference in ACTH secretion between IN DDAVP (day 1) and IN OT prior to IN DDAVP (day 2) (continuous measure); 4) difference in subjective rating of cocaine

craving, stress, depression, anxiety between IN VP (day 1) and IN OT prior to IN DDAVP (day 2; continuous, controlled for last day of use before entering Phase 1); **PHASE 2: Primary outcome:** 1) maximum number of consecutive abstinent days (continuous measure) ; **Secondary outcome:** 1) cocaine using days (continuous). **Covariates/Predictor Variables:** demographics, age, gender; cocaine data (TLFB, 30 days; IN vs. smoked).

3.4.2. Sample size: In PHASE 1, we will enroll a total of 100 participants: 1) Cocaine group (COC): Cocaine-dependent patients seeking treatment (n=50); 2) Control group (CON): Healthy matched controls (n=50), each matched demographically (see 3.1.1). In PHASE 2, we will randomize the 50 COC patients into two groups: 1) Oxytocin group (OT), n=25; 2) Placebo group (PBO), n=25. An independent statistician will perform, and an independent pharmacist will implement the randomization. Individuals will be stratified by route of cocaine use. The randomization will be balanced in blocks of random size 2 and 4 to prevent compromise of the blind.

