The primary outcome was maximum number of consecutive cocaine abstinent weeks. Cocaine use was determined using urine toxicology and TLFB self-report. In a given week, cocaine use was defined as positive if any urine toxicology tests or TLFB self-report was positive (regardless if urine toxicology was negative or missing). Cocaine use was defined as negative if both urine toxicology and self-report were negative or if urine toxicology was missing, the self-report was negative. Cocaine use status was defined as missing if both urine toxicology and self-report were missing. Wilcoxon rank-sum tests were used to examine differences in maximum number of consecutive cocaine abstinent weeks by medication group.

Twenty-six cocaine patients were randomized to 6 weeks of Oxytocin (n=15) or Placebo (n=11). The median (IQR) of the maximum number of consecutive abstinent weeks was 1.0 (1.0 to 1.0) for the OT group and 1.0 (1.0 to 2.0) for the PBO group. The Wilcoxon rank-sum test was not significant, there was no effect of treatment arm on the maximum number of consecutive abstinent weeks ($W = 144.5, p = .67$).

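### Phase 2 randomisation is stratified by route of cocaine use, but the plan adjusts for route only through a data-driven rule with no criterion, and the reported rank test does not use the stratum

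*SAP*

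**What the plan says.** SAP 3.4.2, on the Phase 2 randomisation: "Individuals will be stratified by route of cocaine use". Blocks are of random size 2 and 4.

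SAP Primary Aim 2 analyses the maximum number of consecutive abstinent days with a generalized linear model "with main effect of randomization assignment (OT vs. PBO"). The Protocol repeats this under Specific Aims and Hypotheses. No other term is named.

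SAP 3.4.1 lists the covariates as "demographics, age, gender; cocaine data (TLFB, 30 days; IN vs. smoked"), so route and 30-day use are both candidates. The SAP's Study Assessments text says that the Timeline Follow-Back "estimates cocaine use in the past 30 days at baseline", so the baseline value is planned data.

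SAP 3.4.4 gives the inclusion rule: "The covariates (Section 3.4.1) will be included if they are found to affect outcome measures".

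The closing Primary outcome section of the SAP reports results: "Wilcoxon rank-sum tests were used to examine differences in maximum number of consecutive cocaine abstinent weeks by medication group". It gives 15 patients on oxytocin and 11 on placebo, W = 144.5 and p = .67. It mentions no stratum or covariate.

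**The concern.** Stratified randomisation makes the arms alike on route. An analysis gains from that only if route is in the model or defines the strata of the test. Otherwise the variation due to route stays in the error term, the standard error is too large, and the test rejects less often than its nominal level.

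The inclusion rule does not settle the matter. It names no test, significance level or order, and does not say whether treatment is in the model when the covariates are judged. Treatment only, treatment plus route, and a larger model would each comply with it. The rule therefore does not fix which model is primary.

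The Protocol gives its own reasons to think these variables may matter. Its risk section raises a concern, "especially for intranasal cocaine users, is whether the use of the intranasal approach would serve as a trigger for cocaine use", and both arms use a nasal spray. Eligibility admits a wide range of use, from "Use of cocaine at least 4 days in the past month, with at least weekly use" upward, plus binge users. These are grounds for expecting a link with abstinence, not evidence of its size.

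**Working it through.** **1. The plan's own figure.** Inputs from the SAP Power Analysis: 25 per arm, effect size d = 0.8, two-sided 5%. The normal approximation gives Φ(d√(n/2) − 1.96) = Φ(0.8 × √12.5 − 1.96) = Φ(2.828 − 1.960) = 0.807. The noncentral t gives 0.791. The stated 80% is reproduced to within about a point, and route plays no part in it.

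**2. Type I error when the stratum is ignored.** With route balanced by design, the true variance of the treatment difference is proportional to 1 − r, where r is the share of outcome variance due to route. The treatment-only model estimates it as if proportional to 1. The real two-sided error is then about 2Φ(−1.96/√(1 − r)):

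- r = 0.10: 2Φ(−2.066) = 3.9%. Simulation of 6,000 trials gave 4.0%.
- r = 0.30: 2Φ(−2.343) = 1.9%. Simulation gave 2.1%.

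The direction is conservative. Baseline use is not balanced by design, so leaving it out costs power but does not move the error rate.

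**3. Power with route as a fixed term.** The noncentrality is d/√(1 − r) × √(25 × 25/50), on 50 − 3 = 47 degrees of freedom. For r = 0, 0.10, 0.20, 0.30 it is 2.828, 2.981, 3.162, 3.381, and power is 79.1, 83.1, 87.2, 91.2%.

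**4. Route and 30-day use together.** Simulation of 12,000 trials per cell (standard error at most 0.5 point), with 50 patients randomised within route in random blocks of 2 and 4. Assumed: normal outcome, even route split, R² divided equally between the two covariates, age and gender unrelated to outcome. The SAP's rule is read as a p<0.05 screen of these four covariates, either all in one model or one at a time.

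| Total R² (assumed) | 0 | 0.10 | 0.20 | 0.30 |
|---|---|---|---|---|
| Power, treatment only (%) | 79.0 | 79.3 | 80.1 | 81.3 |
| Power, treatment + route + 30-day use (%) | 78.0 | 81.7 | 86.3 | 90.6 |
| Power, screen in one joint model (%) | 79.2 | 81.4 | 85.7 | 90.3 |
| Power, screen one at a time (%) | 78.4 | 80.0 | 84.1 | 88.7 |
| Type I error, treatment only (%) | 5.0 | 4.4 | 4.1 | 3.5 |
| Type I error, joint screen (%) | 5.3 | 5.2 | 5.7 | 5.6 |
| Type I error, screen one at a time (%) | 5.0 | 4.8 | 5.2 | 5.1 |

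Against fixed adjustment, the screen loses between 0.3 (81.7 − 81.4) and 2.2 points (86.3 − 84.1) when R² > 0, and nothing at R² = 0. Ethnicity was not among the screened covariates.

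**5. At 15 against 11 (illustration only).** With two route strata and blocks of 2 and 4, each stratum can be out of balance by at most 2, so a difference of 4 needs the maximum in both, in the same direction. With 26 patients and a roughly even route split, simulation produced that in 0.34% of randomisations. Under this improbable layout, power at d = 0.8 is 50/49/48/47% unadjusted and 48/52/56/61% with fixed adjustment, for the same four values of R². For a tied weekly outcome with assumed placebo quartiles 1, 1 and 2, van Elteren gains 2.6 to 4.4 points over Wilcoxon at route R² = 0.10 and loses 0.7 to 0.9 if route is not prognostic. With route splits of 8:18 or 6:20 at R² = 0.10, the difference runs from about −3 to +9 points.

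**The case against.** The strongest reply is that the plan does not leave route out. It is a listed covariate, and the inclusion rule covers the analyses that follow it, Primary Aim 2 among them. Read as one ordinary screen, the rule costs at most about 2 points of power against fixed adjustment. This stands, and it limits the point to adjustment that is conditional and undefined. Only the reported Wilcoxon test leaves the stratum out entirely.

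It can also be said that nothing in the documents shows that route or baseline use predicts abstinence after induction, and that baseline use is not a stratification factor. Both are true. The gain is therefore a range over assumed R², and baseline use is a recommended addition, not something the design requires.

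A reader might infer four stronger things that the documents do not support:

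- **That the covariate list is open-ended, because it begins with demographics.** SAP 3.4.4 names these as ethnicity, gender and age. With 30-day use and route, that is a finite list of five.
- **That the open rule produced a favourable choice of model.** If the threshold were left open and the best of five candidate models reported, simulated type I error reaches about 6.5 to 6.7%. The SAP reports one test, which is not significant, and nothing shows selection.
- **That the 15 to 11 split shows the stratified list was not followed.** The documents give neither the number of strata nor how the list was executed, and there are two sites.
- **That a stratified analysis would overturn p = .67.** No outcome data by route are given, so this cannot be assessed.

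**Conclusion.** The point holds in limited form. The factor used to stratify the randomisation is neither a fixed term in the primary model nor part of the reported test, and the rule that might bring it in has no criterion.

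The likely cost is some conservatism and lost power, not a false positive. Against no adjustment at all, fixed adjustment at 25 per arm and d = 0.8 gains about 2, 6 or 9 points at assumed R² of 0.10, 0.20 or 0.30 (81.7 − 79.3, 86.3 − 80.1, 90.6 − 81.3). It costs about 1 point at R² = 0. Against the SAP's own rule, applied as one fixed screen, the gain is 0 to 2 points. These figures rest on a normal outcome, an even route split and an R² that the documents do not supply. The 15 against 11 figures should carry no weight beyond illustration.

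The stated 80% power is unaffected. With 26 patients randomised and not 50, recruitment is the larger power problem: the unadjusted t-test has about 49% power at d = 0.8 with 15 and 11.

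**What to change.** State that the Phase 2 primary model contains treatment and route stratum regardless of significance, with baseline 30-day cocaine use as a further fixed covariate because it is already collected. Delete the conditional inclusion rule for the primary analysis. If a rank test is kept, use van Elteren stratified by route, and note that it does not adjust for baseline use.

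Results are already reported, so none of this can count as pre-specified. Give the route-stratified van Elteren test as one row, labelled as a post hoc sensitivity analysis, beside p = .67 and not in place of it. Mark the corrected SAP sentence as written after the results.

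The cost is small: 1 or 2 degrees of freedom, about 1 point of power at 25 per arm if the covariates are not prognostic, and a possible small loss for van Elteren if the routes are unevenly represented.
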